- 16 PK samples on Day 1 and Week 12 will be taken predose. PK samples at Week 4 and Week 24 will be taken 2 to 6 hours following study drug administration; patients should record the time of study drug administration for these visits. An additional PK sample will be obtained for patients with any AE resulting in unblinding, discontinuation, or SAE.

CONFIDENTIAL

The information contained herein may not be used, disclosed, or published without the written consent of Receptos.

Table 2 Schedule of Assessments – Part A: Optional Blinded Extension, Early Termination, and Follow-up Visits

Procedure	Blinded Extension ¹			Un-scheduled Relapse Visit ⁴	Early Term ⁵	Follow Up Visit 4 weeks after last dose (±5d)
	Day 183 (W26) ² (±1d)	Every 12 weeks ³ (±5d)	End of Study ³			
Clinical laboratory tests ⁶		X	X	X	X	X
Urine/serum pregnancy (women of childbearing potential only) ⁷		X	X		X	X
Coagulation panel			X		X	
Total Ig (IgA, IgG, IgM)						
Complete physical examination			X		X	
Weight			X		X	
Vital Signs	X	X	X	X	X	X
12-lead ECG	X	X	X		X	X
Study drug administration	X	X	X			
Administer study drug at clinic						
Dispense study drug and patient diary		X				
Study drug accountability and compliance check	X	X	X		X	
Brain MRI		X ⁸	X ⁸		X	
EDSS and neurological examination		X	X	X	X	
MSFC and LCLA		X	X	X	X	
MSQOL-54			X		X	
Pulmonary function tests ⁹		X	X		X	
OCT ¹⁰			X		X	
Dermatological (skin) examination			X			
C-SSRS	X	X	X	X	X	X
Standard PK sampling ¹¹					X	
Plasma biomarkers						
Prior/Concomitant therapy	X	X	X	X	X	X
AEs/SAEs	X	X	X	X	X	X

ECG = electrocardiogram, MRI = magnetic resonance imaging, EDSS = Expanded Disability Status Scale, MSFC = Multiple Sclerosis Functional Composite, LCLA = low-contrast letter acuity test; MSQOL = Multiple sclerosis quality of life, OCT = optical coherence tomography, C-SSRS = Columbia- Suicide Severity Rating Scale, PK = pharmacokinetics, AE/SAE = adverse events/serious AE

CONFIDENTIAL

The information contained herein may not be used, disclosed, or published without the written consent of Receptos.

Footnotes to Table 2

- 1 The blinded extension is optional.
- 2 A visit for safety assessments will be performed 14 days after the first dose of study medication.

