- 3 Patients will continue in the optional Blinded Extension period at least until the last patient reaches Week 72 and may continue on blinded therapy until a long-term safety study is available. For patients who continue in the Blinded Extension period beyond the nominal Week 72 visit, the assessments indicated will be repeated at 12-week intervals (with the exception of MRI which will be repeated annually). The End of Study visit will be performed 12 weeks after the previous scheduled visit and after all active patients have received at least 48 weeks of treatment in the Blinded Extension.
- 4 The Unscheduled Relapse Assessment Visit will be conducted in case of a suspected of possible relapse (see [Section 9.1.2.3](#)). After the Unscheduled Relapse Assessment Visit, patients should return to their usual visit schedule.
- 5 Patients who prematurely discontinue study treatment will be asked to complete an Early Termination visit.
- 6 Laboratory tests include Hematology, Chemistry, and Urinalysis
- 7 Urine beta hCG at each visit. If the urine pregnancy test is positive, do not dose and confirm with a serum pregnancy test.
- 8 For patients continuing to the blinded extension, MRI scans will be performed at approximately Weeks 48 and 72, and annually after Week 72. End of Study visit will include an MRI if it corresponds with this schedule.
- 9 Pulmonary function tests will include FEV₁ and FVC measurements at all the above indicated visits. In addition, DLCO will be assessed at the Early Termination visit if the patient prematurely discontinues the study. If any abnormalities occur, they will be followed until such time as resolution is confirmed or no further improvement is expected by the investigator (based on a follow-up period of not less than 3 months).
- 10 If abnormal OCT findings, or visual signs or symptoms of macular edema are observed, a general ophthalmologic examination including eye history, visual acuity, and dilated ophthalmoscopy will also be performed.
- 11 An additional PK sample will be obtained for patients with any AE resulting in unblinding, discontinuation, or SAE.

Table 3 Schedule of Assessments – Part B: Screening, Baseline, and Treatment Period Visits

Visit	Screening	Baseline	Active-Comparator Treatment Period								
		V1	V2	V3	V4	V5	V6	V7	V8	V9	V10
Month	M -1	M1	M1	M3 (W13)	M6 (W26)	M9 (W39)	M12 (W52)	M15 (W65)	M18 (W78)	M21 (W91)	M24 (W104)

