9.1.2.5. Adverse Events of Special Interest

There are a number of potential safety risks associated with RPC1063 administration that are based on the general concerns around immunosuppression (serious and opportunistic infections, malignancies), the safety findings from the Phase 1 clinical study, and the safety profile of the approved S1PR agonist fingolimod and other S1PR agonists. These include serious infections as well as the clinical consequences of its effect on the various organ systems including cardiac and

pulmonary organ systems. Other potential risks observed in the fingolimod experience, although not observed in the Phase 1 clinical trial, include hepatic, ophthalmological and dermatological effects.

Therefore, target AEs of special interest will be closely monitored in the RPC01-201 study. These AEs include infections, malignancies, cardiac (bradycardia and heart conduction abnormalities), pulmonary function (decline in FEV₁, FVC, and DLCO measurements), ophthalmic (macular edema), hepatic (LFTs elevation), and dermatologic (cutaneous malignancy) abnormalities. If any abnormalities occur, they will be followed until such time as resolution is confirmed or no further improvement is expected by the investigator (based on a follow-up period of not less than 3 months). Further details on monitoring of these AEs are provided in [Section 12.4](#).

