9.4.4. Withdrawal of Patients from Study Medication and/or the Study

9.4.4.1. Discontinuation of Study Medication

Reasons for discontinuation include, but are not limited to the following:

- Investigator decision

The Treating Investigator may discontinue study medication if it is determined that it is not safe or in the patient's best interest to receive further treatment. The Medical Monitor should be promptly notified of the decision.

- Noncompliance: after consultation between the investigator, the Medical Monitor, or Study Monitor, and the sponsor when appropriate, a patient may be discontinued from study medication for failure to comply with protocol requirements
- Intercurrent illness: A patient may be discontinued from study medication if, in the judgment of the treating investigator, the patient develops an intercurrent illness or complication that is not consistent with the protocol requirements or that, in any way, justifies discontinuation of study medication.
- Protocol-defined adverse events of special interest (see [Section 12.4](#)):
 - Confirmed AST or ALT >5 times the upper limit of the normal range, confirmed upon retest within 14 days of the original lab value (unless determined by the investigator to not be of hepatic origin)
 - A diagnosis of macular edema, which is new or worsening since baseline
 - FEV1 or FVC <50% of predicted values
- If the patient becomes pregnant
- Sponsor termination or suspension of the study

All patients who discontinue study medication should complete an Early Termination Visit (see [Table 2 \[Part A\]](#) and [Table 4 \[Part B\]](#)). Unless the patient withdraws consent or is lost to follow-up, they will be asked to undergo a follow-up visit 4 weeks after the last dose for the collection of safety data including lymphocyte recovery and to assess their disease status. Alternative treatment for multiple sclerosis (with the exception of medication given in the context of another clinical trial) can be started, if needed, after the early termination visit.

The reason for discontinuation of study medication will be recorded in the clinical records and the patient's eCRF.

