10.2.10. Visits Every 12 Weeks of the Blinded Extension

Patients will continue in the optional Blinded Extension period at least until the last patient reaches Extension Week 48 (nominal Week 72). After the last patient reaches Week 72, patients may continue on blinded therapy until a long-term safety study is available. The following assessments will be performed every 12 weeks of the optional blinded extension, if indicated:

- Blood/urine sampling for the following laboratory tests:
 - Hematology: RBC count, total and differential WBC count (basophils, eosinophils, lymphocytes, monocytes, and neutrophils), platelet count, hemoglobin, hematocrit, MCV, MCH, and MCHC
- Note: All total WBC and differential WBC counts will be blinded during the study.

- Blood chemistry: sodium, potassium, chloride, calcium, magnesium, phosphate, blood urea nitrogen, random glucose, albumin, alkaline phosphatase, creatinine, SGPT/ALT, SGOT/AST, GGT, amylase, total bilirubin, conjugated bilirubin,. Abnormal laboratory parameters inconsistent with clinical presentation of MS or suspicious of underlying medical condition should be repeated for accuracy. If an increase of amylase above the clinically notable value (≥ 300 U/L) is observed at any post randomization visit, lipase should be tested to determine the origin of elevated amylase (pancreatic versus extra pancreatic)
- Urine beta-hCG (females of childbearing potential only). If the urine pregnancy test is positive, do not dose and confirm with a serum pregnancy test.
- Vital signs: body temperature, blood pressure and heart rate
- 12-lead ECG
- Dispense study drug and patient diary
- Review study drug accountability and compliance
- EDSS and neurological examination
- MSFC AND LCLA
- Pulmonary function tests including FEV₁ and FVC measurements
- Suicidality assessment using the C-SSRS
- Record concomitant therapy
- Record AEs/SAEs

MRI assessments during the blinded extension:

- Brain MRI at approximately Weeks 48 and 72
- After Week 72, brain MRI will be performed annually

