OCT will be performed as scheduled in [Table 1](#) and [Table 2](#) (Part A), and [Table 3](#) and [Table 4](#) (Part B). If there is a suspicion of macular edema, then general retinal exams including eye history, visual acuity, and dilated ophthalmoscopy will be obtained. A general ophthalmologist can do the examination, although a retinal specialist would be preferred to do the exams wherever possible.

Dermatological (Skin) Examination

Dermatological (skin) evaluations will be performed as part of the physical exam at screening, and then every 6 months in Part A and yearly in Part B, as scheduled in [Table 1](#) and [Table 2](#) (Part A), and [Table 3](#) and [Table 4](#) (Part B). Dermatological (skin) evaluations will be performed by the treating investigator or medically qualified designee. Patients with any suspicious finding noted during the examination will be referred to an appropriately qualified dermatologist for evaluation and treatment, if warranted.

Suicidality Assessment

Suicidality will be assessed using the C-SSRS ([Posner, 2011](#)) at all study visits during Part A and Part B. It will be self-administered through a validated IVRS.

Monitoring of AEs and SAEs

Throughout the course of the study, Part A (both periods) and Part B, every effort must be made to remain alert to possible AEs or SAEs. Refer to [Section 12](#) for definitions of AEs/SAEs, monitoring and reporting. Refer to [Section 12.4](#) for AEs of special interest.

Monitoring of Concomitant Therapy

The use of concomitant medication and procedures will be monitored throughout the study in Part A (both periods) and Part B. Refer to [Sections 9.5.7](#) and [9.5.8](#) for prohibited concomitant therapies.

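### Part A skin examinations: Table 2 omits the one required at early termination, and schedules none between Week 24 and an End of Study visit with no latest date, although 11.2.1 says every 6 months

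*Protocol*

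**What the plan says.** Protocol 11.2.1 sets the frequency: at screening, "and then every 6 months in Part A and yearly in Part B, as scheduled in" Tables 1 and 2 for Part A and Tables 3 and 4 for Part B. Section 12.4 gives a shorter list for Part A (screening and 6 months) and adds that patients who discontinue early are examined at end of treatment. Section 10.5 lists a dermatological examination at the Early Termination visit, as an item separate from the physical examination, without restricting it to one part of the study.

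The row "Dermatological (skin) examination" is marked at Screening and Week 24 in Table 1. In Table 2 it is marked at End of Study only. In Table 4, the Part B counterpart, it is marked at Early Termination.

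Section 9.4.4.1 states: "All patients who discontinue study medication should complete an Early Termination Visit". For Part A it points to Table 2.

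Section 10.2.10 introduces its list with "The following assessments will be performed every 12 weeks of the optional blinded extension, if indicated"; neither a skin nor a physical examination is on it. Footnote 3 to Table 2 says patients "may continue on blinded therapy until a long-term safety study is available", and that beyond Week 72 the marked assessments recur at 12-week intervals "with the exception of MRI which will be repeated annually". On the last visit it says: "The End of Study visit will be performed 12 weeks after the previous scheduled visit", once all active patients have had at least 48 weeks in the extension. Section 10.2.11 adds that a long-term study must also be available.

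**The concern.** Section 9.1.2.5 includes "dermatologic (cutaneous malignancy) abnormalities" among the adverse events of special interest, and 12.4 assigns the skin examination to monitor for them. The protocol states two rules for this in Part A, 6-monthly and at early discontinuation, and Table 2 schedules neither.

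At early termination, a site working from Table 2 would not do the dedicated examination. For a patient who stops before Week 24 it would be the only one after baseline.

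In the extension, every continuing patient is on RPC1063, because placebo patients are re-randomized to it. These patients are scheduled for fewer skin examinations than 11.2.1 states, and the interval depends on when the slowest patient reaches Week 72 and when another study opens. MRI has explicit dates for this period and an annual rule afterwards. The skin examination has neither.

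**Working it through.** **1. The places side by side (protocol, Part A unless noted)**

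| Place | To Week 24 | Extension | Early termination |
|---|---|---|---|
| 11.2.1 | Screening, then 6-monthly | 6-monthly | not stated |
| 12.4 | Screening, 6 months | none | required |
| Tables 1 and 2 | Screening, Week 24 | End of Study only | blank |
| 10.2.10 and 10.2.11 | – | none at 12-weekly visits; End of Study | – |
| 10.5 | – | – | listed |
| Table 4 (Part B) | – | – | marked |

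The OCT row directly above the skin row in Table 2 is marked at both End of Study and Early Termination, so the columns can be read and the blank skin cell is in the Early Termination column.

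**2. The plan's own duration.** 24 weeks controlled + at least 48 weeks extension = at least 72 weeks. This reproduces the figure in 9.1 and 9.3.

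**3. Gap in the extension.** Visits after Week 24 are 12-weekly: Weeks 36, 48, 60, 72, 84, 96. Gap = End of Study week − 24. Part B (Table 3, Months 12 and 24) has an interval of 52 weeks.

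| End of Study | Gap | Against Part B's 52 weeks |
|---|---|---|
| Week 72 | 72 − 24 = 48 | 4 shorter |
| Week 84 | 84 − 24 = 60 | 8 longer |
| Week 96 | 96 − 24 = 72 | 20 longer |

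Part B's interval is exceeded once End of Study falls after Week 24 + 52 = 76. Six months is about 26 weeks, so even the shortest gap is nearly twice the stated interval.

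**4. How likely the longer gaps are.** A patient whose own Week 72 visit has passed before both End of Study conditions are met has End of Study at Week 84 at the earliest, a gap of at least 60 weeks. Section 13.6.7 expects about 45% of patients to have completed 12 weeks of treatment about one month before enrollment ends. Taking a month as about 4 weeks, those patients are at least 12 + 4 = 16 weeks ahead of the last one enrolled. When that last patient reaches Week 72, they are at Week 88 or later. Their next scheduled visit is Week 96 or later, a gap of at least 72 weeks even if the long-term study is already open. This is a planning estimate. It assumes the last-enrolled patients enter the extension, and it applies only to early enrollees who also continue. The number affected cannot be computed, because extension uptake and the opening date of the long-term study are not given.

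**5. Early termination.** At the 15% dropout assumed in 13.2, 0.15 × 210 = 31.5, so about 32 patients would leave before Week 24. About 0.15 × 140 = 21 of them would be on RPC1063 if dropout is equal across arms. Under that assumption this is an upper count of Early Termination visits, since patients lost to follow-up or withdrawing consent may have none.

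**The case against.** **Early termination loses little.** Sections 10.5 and 12.4 both bind Part A, and Table 2 marks a complete physical examination at that visit, which 10.5 and 11.2.1 define as including skin. The skin check is done by the treating investigator or a designee, so it is not a separate specialist procedure. This stands: the practical loss is small, and what remains is one cell that contradicts two instructions. The 15% is also a planning assumption that actual dropout could exceed, and it counts people leaving, not people left unexamined.

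**The blank may come from redaction.** Some rows in Table 1 are blank where the text requires the assessment. That is a fair caution, but it is implausible here. The End of Study mark in the same row survives, the OCT row above is intact, and skin examinations are redacted nowhere else.

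**The extension schedule is consistent and may be deliberate.** Table 2, 10.2.10, 10.2.11 and 12.4 agree, and OCT, weight and the physical examination also skip the 12-weekly column. It is true that 11.2.1 is the outlier, so sites should not diverge. But 11.2.1 states an interval for skin and none for OCT, and no physical examination at the 12-weekly visits fills the gap. The Part A SAP still describes a 24-week extension (Weeks 25 to 48), under which Week 24 and a Week 48 end visit would meet a 6-monthly rule. That suggests an oversight when the extension was lengthened, although this is inference.

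**48 weeks is acceptable.** Part B uses yearly examinations at the same doses, and no dermatological effect was seen in Phase 1. This is conceded for 48 weeks alone. The synopsis plans for the study to end in May 2017, which is a loose calendar bound but not a rule on the examination interval. Adverse events are recorded at every extension visit and suspicious findings are referred to a dermatologist, so monitoring is thinner than stated, not absent.

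**Conclusion.** Both mismatches hold. The blank Early Termination cell in Table 2 contradicts 10.5, 12.4 and Table 4; its practical effect is limited. The extension point carries more weight: the schedule does not deliver the 6-monthly examinations in 11.2.1, the gap after Week 24 is at least 48 weeks, and the protocol sets no maximum. If enrollment runs as planned and late enrollees continue, early enrollees who also continue face about 72 weeks or more, against 52 in Part B at the same doses. The objection is to an interval without a limit, not to 48 weeks as such. The matter concerns safety ascertainment for an adverse event of special interest and should be corrected; it does not touch efficacy, alpha or sample size.

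**What to change.** Mark the dermatological examination in the Early Termination column of Table 2. Then bring 11.2.1, 12.4, Table 2 and 10.2.10 into agreement by one of two routes.

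- **Preferred:** add the examination at the existing Week 48 and Week 72 visits and every 24 weeks after that, which delivers the 6-monthly interval. Added examinations per continuing patient before End of Study: one if End of Study is Week 72 (at Week 48), two if it is Week 84 or 96 (at Weeks 48 and 72).
- **Minimum:** correct the frequency in 11.2.1 and schedule the examination at least yearly, for example at Week 72 and every 48 weeks after that, so that the interval is capped. Added examinations: none if End of Study is Week 72, one if it falls from Week 84 to Week 120.

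The cost is one mark in Table 2, the wording corrections, and brief examinations by the treating investigator or designee at 12-weekly visits that already take place.

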11.2.2. Laboratory Safety Assessments

██████████ will analyze the samples. Further details of the procedures to be followed for sample collection, storage, and shipment will be documented in a laboratory manual.

Additional and repeat laboratory safety testing may be performed at the discretion of the Investigator.

The following laboratory tests will be performed to assess the safety profile of RPC1063:

- Routine safety laboratory tests:
 - Hematology - RBC count, total and differential WBC count (basophils, eosinophils, lymphocytes, monocytes, and neutrophils), platelet count, hemoglobin, hematocrit, MCV, MCH, and MCHC. Total WBC and all differential WBC counts will be blinded information for the treating investigator after the onset of study treatment.
 - Chemistry - sodium, potassium, chloride, calcium, magnesium, phosphate, blood urea nitrogen, random glucose, hemoglobin A1c, albumin, alkaline phosphatase, creatinine, SGPT/ALT, SGOT/AST, GGT, amylase, total bilirubin, conjugated bilirubin as scheduled in [Table 1](#) and [Table 2](#) (Part A), and [Table 3](#) and [Table 4](#) (Part B). In addition, the following parameters will be assessed at baseline and every 6 months of Part B: total cholesterol, triglycerides, HDL and LDL. Abnormal laboratory parameters inconsistent with clinical presentation of MS or suspicious of underlying medical condition should be repeated for accuracy. If an increase of amylase above the clinically notable value (≥ 300 U/L) is observed at any post randomization visit, lipase should be tested to determine the origin of elevated amylase (pancreatic versus extra pancreatic)
 - Urinalysis - leukocytes, specific gravity, bilirubin, blood, glucose, ketones, pH, protein, and urobilinogen
- The central laboratory will analyze routine blood samples. Blood samples taken at the screening visit are to be in the fasting state. Blood samples taken at subsequent visits are recommended to be in the fasting state. Details regarding collection of samples, shipment of samples, reporting of results, laboratory reference ranges, and alerting abnormal values will be supplied to the site before site initiation in a study laboratory manual. The results of the analysis will be made available to each site by the central laboratory, at the earliest, 48 hours after receipt of the samples by the central laboratory.
- Investigators will be asked to comment on those abnormalities on the respective laboratory result page, including a notation of the clinical significance of each abnormal finding in the patient's source documents. The laboratory sheets will be filed with the patient's source documents. Abnormal laboratory values should not be recorded on the AE eCRF; however, any diagnoses (or signs or symptoms if a diagnosis is not possible) associated with the abnormal findings should be recorded on the AE eCRF.
- Pregnancy test: serum beta-hCG must be performed at screening (Part A and Part B) in women of childbearing potential; urine beta-hCG will be performed in women of childbearing potential at each visit (Part A and Part B), and if positive, do not dose, and confirm with a serum pregnancy test.
- Coagulation panel: PT and PTT. To be performed at screening, at Week 24/end of study of Part A and Month 24/end of study of Part B, and at follow-up visits.
- sTSH: To be performed at screening, at Week 24/end of study of Part A, and yearly during Part B.

- Serology testing will be performed at screening of Part A and Part B to determine the patient's immune status with respect to the following viruses:
 - VZV
 - HIV antibodies
 - anti-hepatitis A virus IgM
 - HBsAg and HBcAg IgM
 - anti-HCV IgG or IgM.

Patients who are negative for VZV IgG antibodies at screening can undergo appropriate varicella zoster vaccination and be enrolled 30 days after vaccination has been completed. Patients testing positive for HIV or for serological markers of acute or chronic hepatitis A, B, or C will be excluded from the study unless they are indicative of prior hepatitis B vaccination or cured hepatitis A or B and accompanied by normal liver transaminase values.

- Syphilis RPR: Patients must have a negative RPR result to be enrolled or, in the event of a false positive result on RPR, a negative treponeme-specific test performed at the central laboratory.
- TB test: to be assessed using the purified protein derivative test, QuantiFERON Gold, or other interferon gamma release assay (as locally available), and CXR at screening of Part A and Part B. All testing must be completed prior to administration of study drug on Day 1.

